Elvitegravir (EVG) Cerebrospinal Fluid (CSF) Pharmacokinetics in HIV-Infected Adults

Investigators:

[name] [name], PhD

Clinical Trials Identifier:

NCT02251236

Last Update:

2 July 2014

UCSD Human Research Protections Program New Biomedical Application RESEARCH PLAN

Instructions for completing the Research Plan are available on the HRPP website. The headings on this set of instructions correspond to the headings of the Research Plan. General Instructions: Enter a response for all topic headings. Enter "Not Applicable" rather than leaving an item blank if the item does not apply to this project.

Version date: 9/30/2013

PROJECT TITLE

Elvitegravir (EVG) Cerebrospinal Fluid (CSF) Pharmacokinetics in HIV-Infected Individuals

PRINCIPAL INVESTIGATOR

[name]. Professor of Medicine University of California, San Diego

FACILIZIES ir (EVG) Cerebrospinal Fluid (CSF) Pharmacokinetics in HIV-Infected Individuals

The study will be conducted locally at the UCSD AntiViral Research Center (AVRC), [name] and the HIV Neurobehavioral Research Program (HNRP), [name].

Document Date: 7/2/2014

ESTIMATED DURATION OF THE STUDY

The enrollment period is anticipated to be approximately 18 months with final results approximately 24 months after study initiation. Subject participation will be approximately 24 weeks.

5. LAY LANGUAGE SUMMARY OR SYNOPSIS (no more than one paragraph)

The proposed project is a single dose, single arm, open-label, multicenter, phase IV pharmacokinetic study with the primary aim of describing cerebrospinal fluid (CSF) concentrations of elvitegravir (EVG), an HIV integrase inhibitor. Stribild is an FDA-approved, multiclass combination drug with potent antiretroviral activity against HIV-1. Stribild is a tablet containing four drugs, one of which is EVG. The study population will be HIV-1 infected study subjects who are naive to EVG. The study will enroll 14 subjects at three sites in the United States, who will be given Stribild over a period of approximately six months. Blood draws, urine collection and lumbar punctures will be performed after screening, to generate 22 on-treatment CSF-blood specimen pairs. Pharmacokinetic (PK) analysis will provide a small-sample estimate of distribution of EVG into CSF. HIV Dementia Scale scores will also be measured. The study will recruit approximately 7 subjects at UCSD.

SPECIFIC AIMS 6.

Primary:

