9. RESEARCH DESIGN AND METHODS

The proposed project is a single dose, single arm, open-label, multicenter, phase IV pharmacokinetic study. This study plans to enroll 7 HIV-infected, EVG Naïve subjects at our site and 14 at all sites.

The goals of the study are to (1) describe the population pharmacokinetics of elvitegravir in CSF, and (2) determine the impact of StribildTM on suppressing HIV RNA in CSF, blood-brain barrier permeability, and HIV Dementia Scale scores. No published studies have addressed the following questions: 1) What are the concentrations of elvitegravir in the CSF in patients with HIV-1 disease? 2) Do these concentrations exceed the 95% inhibitory concentration (IC95) for wild-type HIV-1? 3) How does StribildTM affect blood-brain barrier permeability and HIV Dementia Scale scores? We will address these questions in a prospective, open-label treatment trial of HIV-infected, treatment-naive patients.

Even though this is primarily a pharmacokinetic study of FDA-approved drugs, adverse events will likely occur. According to the package insert, the most common adverse reactions are nausea (16%), diarrhea (12%), abnormal dreams (9%), headache (7%), fatigue (4%), rash (3%), insomnia (3%), and dizziness (3%).

Laboratory abnormalities can also occur, including elevations in creatine kinase (7%), elevated amylase (3%), and hematuria (3%). Serious adverse events, including lactic acidosis and severe hepatomegaly, have been reported but are uncommon. The standard regimen of StribildTM will be used. If a regimen change occurs during the course of the project, participation will be discontinued. Patients will be carefully screened and those with pre-conditions, such as morbid obesity or hepatitis B virus co-infection, will be excluded.

HIV-1 infected patients who are willing to initiation antiretroviral therapy and who are naive to the components of StribildTM will be the study population. StribildTM has been recently added into the DHHS Guidelines as an option for the first-line therapy. The study will enroll 14 subjects to generate 22 on-treatment CSF-blood specimen pairs, which is sufficient to provide a small-sample estimate of distribution of EVG into CSF. A tabular schedule of assessments is provided below.

Assessment	Screening	Baseline	Week 2	Week 8	Week 16	Week 24
Time window (days)	-28 to -1	0	12-20	49-63	105-119	161-175
Informed consent	X					
Brief assessment	X		X			
Eligibility assessment	X					
Full assessment		X				X

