- vi) Estimated glomerular filtration rate (eGFR)
- vii) For women of childbearing potential: Serum or urine pregnancy test.
- viii) HIV RNA in blood plasma
- ix) HIV RNA in CSF
- x) CSF total leukocyte count and differential, CSF erythrocyte count, CSF total protein, CSF albumin, CSF glucose
- xi) Lymphocyte subsets in blood (including CD4+ and CD8+ T-cell absolute counts and percentages)
- e) Pharmacokinetics: Detailed instructions for performing the pharmacokinetic studies are detailed in the *PK Sample Collection and Processing Document*. Briefly:

StribildTM containing elvitegravir (EVG) 150 mg will be administered in the morning after breakfast, *e.g.* 9:00 am, for study days 1-14. The precise times of dosing on days 11, 12 and 13 shall be recorded.

On the morning of study day 14, subjects will be instructed to hold their morning dose and will report to the clinical research center at approximately 8:00 a.m. An indwelling catheter will be placed in one arm of the subject for serial PK sampling. StribildTM will be administered later that morning immediately after a meal and the precise time of drug administration will be recorded.

Blood samples will be collected prior to StribildTM dosing, and at 2, 4, and 6 hours following StribildTM administration. The catheter will then be removed and a lumbar puncture will be performed within 1 hour of the last blood sampling (~ 7 hours after StribildTM dosing). Subjects will then be discharged from the clinical research center.

- f) 5 mL of blood serum, 10 mL of blood plasma, 5 mL of whole blood, 5 mL of urine, and 8 mL of CSF will be stored at -70°C. An aliquot of peripheral blood mononuclear cells will be stored at -150°C.
- g) Subjects will be strongly encouraged to have an appointment with a primary care provider scheduled within a week prior to the final study visit to obtain a prescription and allow for clinical dispensing of continuing antiretroviral therapy.

Premature Discontinuation

Subjects who prematurely discontinue study treatment will undergo an assessment similar to the one detailed for Week 24 with the following exceptions.

- a) The visit will not include lumbar puncture.
- b) The visit will not include PK assessment.
- c) The visit will not include drug dispensing.
- d) Following up with a primary care provider will be discussed with the study subject.

Off-Drug Requirements

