Additional safety monitoring and reporting of Serious Adverse Experiences (SAEs) continues to be required upon completion or discontinuation of study treatment regardless of whether a protocol follow-up period is scheduled to occur. Adverse experiences occurring during the immediate 8-week period after the last dose of study treatment which meet SAE Reporting Requirements must be reported to the sponsor and the Institutional Review Board (IRB). If the study subject discontinues study treatment, after 8 weeks OFF study treatment,

there are 4 types of events which must be reported to the sponsor and the IRB if the relationship to the study treatment is assessed by the site physician as definitely, possibly, or unable to judge: DEATHS, NEW ONSET CANCERS, CONGENITAL ANOMALIES, PERMANENT DISABILITIES. The study nurse will call the study subject eight weeks after the last study visit to determine if an SAE has occurred.

STATISTICAL CONSIDERATIONS

General Design Issues

The first objective of this study is to evaluate the CSF pharmacokinetics of EVG. This will be accomplished by evaluating HIV-1 infected, treatment-naive subjects. In this single arm, open-label study, within-subject differences in pharmacokinetics parameters at week 2 and 24 will be analyzed, as each subject will serve as his/her own control. For the secondary objective, which is to evaluate the effect of StribildTM on the permeability of the blood-brain barrier and HIV Dementia Scores, we will consider within-subject differences in a similar manner to analyses for the primary objective.

Pharmacokinetic analysis

Two methods, one model-independent and one model-dependent analyses, will be undertaken in this study. The use of these two methods of analysis will serve as validation. For the model-independent method, total and unbound plasma concentrations and total CSF concentrations will be used to calculate a CSF/plasma ratio, based on individual subject concentration-time profiles. The model-dependent method will fit a population hierarchical mixed-effect model to the data including clinical outcomes. Relevant hypotheses can be tested using the likelihood ratio test. Individual pharmacokinetic parameters can be estimated by empirical Bayesian methods.

Endpoints

Primary endpoints

a) Plasma and CSF total/unbound concentrations of EVG over 2- and 24-week treatment periods

Secondary endpoints

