- a) Proportion HIV RNA levels below the lower limit of quantitation in CSF and plasma from 2- and 24-week assessments.
- b) Changes in CD4+ T-cells at baseline and week 24.
- c) Changes in blood-brain-barrier permeability as indicated by CSF-to-serum albumin ratio between baseline and either week 2 or week 24.
- d) Changes in HIV Dementia Scale scores between baseline and week 24.

Sample Size and Accrual

Based on estimates from ING116070, assuming within-subject coefficients of variation between 30 and 40%, with a type I error of 0.05 and 90% power, a sample size of 14 would be sufficient to detect a minimum of 50% change in the CSF concentration of EVG using a two-sided paired t-test.

Any subject who prematurely discontinues study participation prior to completing at least one on-treatment PK assessment will be replaced by another subject.

Drug Regimens, Administration and Duration:

Days 1-14: Give StribildTM (150 mg EVG, po q AM)

Day 14: First PK assessment (PK1)

Days 15-168: Continue StribildTM (150 mg EVG, po q AM)

Day 168: Second PK assessment (PK2)

StribildTM (150 mg EVG, po q AM). With the exception of PK days, can be administered as a single dose in the morning, immediately after breakfast.

At PK assessment visits, subjects will be asked to hold all study drugs. Doses will then be administered in the clinical research center under direct observation by study staff.

Drug Formulations

a. StribildTM (150 mg elvitegravir, 150 mg cobicistat, 200 mg emtricitabine, and 300 mg tenofovir disoproxil fumarate): green, capsule-shaped, film-coated tablets. Store at room temperature (15-30 °C) (59-86 °F)

Drug Supply, Distribution and Pharmacy

Dispensing and monitoring drug-taking behavior

a. Adherence will be self-reported and documented by project staff on appropriate CRFs. Subjects will be asked to bring medication bottles to each visit.

Study supply acquisition

a. The study treatment will be supplied by Gilead Sciences to each study site and will then be dispensed by each site's research pharmacy.

Accountability

- a) The study pharmacist will maintain complete records of all study medications received and subsequently dispensed.
- b) All unused study medication will be returned to the study pharmacy and discarded following standard operating procedure.

Concomitant Medications

Precautions

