a) STRIBILD is NOT recommended for coadministration with: emtricitabine or tenofovir DF (ATRIPLA, COMPLERA, EMTRIVA, TRUVADA, VIREAD); products containing lamivudine (COMBIVIR, EPIVIR, EPIVIR-HBV, EPZICOM, TRIZIVIR) or adefovir dipivoxil (HEPSERA); or ritonavir (NORVIR, KALETRA).

Contraindications

a) Coadministration of STRIBILD is contraindicated with drugs that are highly dependent on CYP3A for clearance and for which elevated plasma concentrations are associated with serious and/or life-threatening events, *e.g.* alfuzosin, rifampin, ergo derivatives, cisapride, St. John's wort, lovastatin, simvastatin, sildenafil, triazolam, oral midazolam. Specific case-by-case exemptions may be considered by the study investigators.

Management of Selected Toxicities

New Onset or Worsening Renal Impairment

a) Renal impairment, including acute renal failure and Fanconi syndrome, has been reported with the use of STRIBILDTM. If renal impairment occurs as indicated by a decrease of estimated creatinine clearance below 50 mL/min, study treatment will be discontinued. Subjects will be followed off treatment with evaluations as per section 4.2 of the master protocol.

Lactic Acidosis/Severe Hepatomegaly with Steatosis

a) Lactic acidosis and severe hepatomegaly with steatosis, including fatal cases, have been reported with the use of tenofovir DF, a component of STRIBILD, in combination with other antiretrovirals. Treatment with STRIBILD should be suspended in any subject who develops clinical or laboratory findings suggestive of lactic acidosis or pronounced hepatotoxicity.

Bone Effects, Fat Redistribution, and Immune Reconstitution Syndrome

- a) Decreases in bone mineral density, redistribution/accumulation of body fat, and immune reconstitution syndrome have been reported in patients treated with STRIBILDTM, which may necessitate further evaluation and treatment.
- b) Any Grade 2 or higher symptoms or laboratory abnormalities will result in termination of the subject from the study (see Section 4.2 of the master protocol for post-treatment evaluations).
- c) If a subject discontinues the study drugs prior to the pharmacokinetic sampling on day 14, s/he will be replaced in the original sample size.

Criteria for Treatment Discontinuation

- a) The subject or legal guardian refuses further treatment and/or follow-up evaluations.
- b) The investigator determines that further participation would be detrimental to the subject's health.

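### The 90% power at n = 14 needs 14 complete Week 2/Week 24 CSF pairs, but the plan's 22 specimens imply 8 (at most 11), so 90% is not held over CV 30–40%

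*Combined protocol and SAP*

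**What the plan says.** All references are to the combined protocol and SAP.

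- **Section 9, Sample Size and Accrual:** "assuming within-subject coefficients of variation between 30 and 40"%, two-sided type I error 0.05 and 90% power, "a sample size of 14 would be sufficient to detect a minimum of 50% change in the CSF concentration of EVG" by a paired t-test. No allowance for loss is stated. Nor are the scale (raw or log), the direction of the change, or the SD of the paired difference.
- **Section 9, General Design Issues:** this identifies the pair: "within-subject differences in pharmacokinetics parameters at week 2 and 24 will be analyzed".
- **Section 9, design description:** "The study will enroll 14 subjects to generate 22 on-treatment CSF-blood specimen pairs". The synopsis in Section 5 repeats the number: "to generate 22 on-treatment CSF-blood specimen pairs". The document calls this enough for a small-sample estimate of distribution into CSF.
- **Section 9, replacement:** a subject is replaced only if lost "prior to completing at least one on-treatment PK assessment will be replaced by another subject". The toxicity subsection agrees: a subject who "discontinues the study drugs prior to the pharmacokinetic sampling on day 14, s/he will be replaced in the original sample size".
- **Section 9, Premature Discontinuation:** "The visit will not include lumbar puncture", and there is no PK assessment at that visit either.

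**The concern.** The two numbers describe different things and are never connected. Fourteen is the count for a paired test, so it has to mean 14 subjects with both CSF values. Twenty-two is the planned specimen yield, six short of two per subject. A subject lost after Week 2 is neither replaced nor sampled on leaving, so each such loss removes a pair from the test.

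This is the only power figure given for the CSF concentration endpoint. If it rests on more pairs than the specimen plan supplies, a null Week 2 versus Week 24 comparison could be read as carrying 90% power when it does not.

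**Working it through.** **Inputs.** Two-sided alpha 0.05, power 90%, change 0.50, within-subject CV 0.30 to 0.40 and n = 14 (Sample Size and Accrual); 22 specimens from 14 subjects (synopsis and design description); two on-treatment PK visits per subject (Drug Regimens). Assumption, because the plan is silent: raw scale, equal SD at both visits, SD of the difference = √2 × CV.

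**Step 1: reproduce 14.** The normal-approximation count of pairs is n = (1.960 + 1.282)² / d², with d = 0.50 / (√2 × CV).

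- CV 40%: d = 0.884, n = 13.45, rounded up to 14.
- CV 30%: d = 1.179, n = 7.57, rounded up to 8.

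So 14 matches complete pairs at the upper CV with nothing added for loss. With the exact (noncentral t) calculation the counts are 16 and 10, and 14 pairs at CV 40% give 86%.

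**Step 2: complete pairs implied by 22 specimens.** Let m be the number of subjects giving at least one specimen, s1 those giving one and s2 those giving two. Then s1 + s2 = m and s1 + 2·s2 = 22, so s2 = 22 − m.

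- m = 14: 8 pairs
- m = 13: 9 pairs
- m = 12: 10 pairs
- m = 11: 11 pairs, the maximum (22/2)

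The replacement rule aims at m = 14, so 8 is the count most consistent with the plan.

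**Step 3: power for a 50% change, exact t, on the reading that reproduces 14.**

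| CV | 8 pairs | 11 pairs | 14 pairs |
|---|---|---|---|
| 30% | 82% | 94% | 98% |
| 35% | 69% | 85% | 94% |
| 40% | 58% | 75% | 86% |

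The miss rate at CV 40% is 42% with 8 pairs and 25% with 11, against the stated 10%; at CV 30% it is 18% and 6%. Eight pairs reach 90% only up to a CV of about 26%, and eleven up to about 32.5%.

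**Step 4: change detectable with 90% power (CV 30% to 40%).** With 8 pairs it is 57% to 76%; with 11, 46% to 61%; with 14, 40% to 53%.

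**Step 5: other readings of the unstated SD and scale, exact t.**

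| Reading | 8 pairs, CV 30% | 8 pairs, CV 40% | 11 pairs, CV 40% |
|---|---|---|---|
| Raw, SD of difference = CV | 98% | 86% | 96% |
| Log scale, halving | 98% | 87% | 97% |
| Log scale, 50% increase | 66% | 44% | 61% |

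The log rows use SD of the difference = √(2·ln(1 + CV²)). The first two readings need only 7 to 9 pairs by exact t and so do not explain 14. The third needs exactly 14 at CV 30% (power 92%) but 21 at CV 40%.

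**The case against.** **Part of the gap comes from the method.** Fourteen is reproduced by the normal approximation, while the shortfall is measured by exact t. Kept on the approximation, 8 pairs give 91.5% at CV 30% and 70.5% at CV 40%; 11 pairs give 97.4% and 83.4%. This stands as a point about attribution: at CV 30% the deficit with 8 pairs disappears under the approximation. Exact t is the right calculation for so few pairs, and on either method neither 8 nor 11 pairs reach 90% at CV 40%.

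**The reading is not unique.** The plan says 14 is sufficient, not minimal, so a favourable SD could have been intended, and the shortfall would then be small: 86–87% with 8 pairs at CV 40%, and 91–92% with 9. This stands, and it is why the power figures are conditional. The other reading that gives 14, a 50% increase on the log scale, makes the shortfall worse.

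**Twenty-two may be a minimum yield.** No attrition rate is given. If more specimens are obtained, pairs rise one for one. That is possible, but 22 is the only yield the plan states.

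**Little depends on the test.** The primary aim is descriptive, and the planned mixed-effect model can use subjects seen once. Both are true and limit the consequence. But the 90% is claimed for the paired t-test, and no power is given for the model.

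**A fuller derivation may sit elsewhere,** in the master protocol or the study cited for the CVs. It could settle the scale and SD, but the two figures would still need reconciling in this document.

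**Conclusion.** The concern holds. The stated 90% rests on 14 complete pairs, and the plan's own specimen count with its replacement rule implies 8, with 11 as the ceiling. On the raw-scale reading that reproduces 14, 8 pairs fall below 90% throughout CV 30–40%, and 11 pairs do so above about CV 33%. Eight pairs at CV 40% miss 90% on every reading tried, by a few points on the favourable ones and by more than 30 points on the reading that reproduces 14.

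The size rests on the assumed scale and SD of the difference, which the plan should supply. The direction does not. The descriptive primary aim is unaffected. This should be fixed, because a stated property of the design does not match its sampling plan.

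**What to change.** Rewrite the sample-size paragraph, with enrolment unchanged:

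1. Reconcile the 22 specimens with the 14 subjects, and state the expected number of complete Week 2/Week 24 CSF pairs.
2. State the scale, the direction of the change and the SD of the paired difference, with its link to the quoted CVs.
3. Restate power or detectable change for 8 to 11 pairs over CV 30–40%, by exact t. On the reading that reproduces 14, this is 58–82% power with 8 pairs and 75–94% with 11.

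As an option, add a precision statement for the descriptive aim. For example, if all 14 subjects exceeded the IC95, the exact 95% lower limit for that proportion would be 0.025^(1/14) = 0.768, or 77%.

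The cost is one reworded paragraph and a less favourable power figure. No patients, procedures or samples are added.

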- a) The study coordinator will call study subjects at Weeks 8 and 16 (and more often at their discretion) to inquire about signs or symptoms of adverse effects as well as medication adherence. Results will be recorded on a CRF. If any symptoms are reported, the subject will be asked to come to the clinic to be evaluated by the study nurse and investigator (see Section 6.6 of the master protocol).
- b) Drug dispensing: Eight weeks of study drug will be dispensed at Weeks 8 and 16.
- c) HIV RNA in plasma: Study subjects will be asked to return to their primary care provider to obtain a measurement of HIV RNA in blood plasma per routine clinical care. This is anticipated to occur after approximately 12 weeks of treatment. Study subjects will be asked to bring a copy of the lab report to the research center. Alternatively and with the consent of the study subject, the research nurse will obtain the value from the clinic.

6) Week 24 Assessments

- a) A complete medical history and physical examination will be performed:
 - i) Prior diagnoses including liver disease, renal disease, fracture, osteoporosis, allergies, drug reactions, and most recent menses.
 - ii) Current symptoms including those of an active systemic illness (e.g., fever) and bleeding or easy bruising.
 - iii) Prescription and non-prescription medications taken within 14 days prior to entry.
 - iv) Vital signs, including temperature, blood pressure, and pulse rate, height, weight, and waist circumference.
- b) The HIV Dementia Scale will be performed.
- c) 75 mL of blood and 15 mL of urine will be collected by standard methods. 15 mL of cerebrospinal fluid (CSF) will be collected by lumbar puncture using aseptic technique and an atraumatic needle. Collection will follow a specific schedule as detailed in detailed in the *PK Sample Collection and Processing Document* and summarized in section 4.2.2 of the master protocol.
- d) The following laboratory tests will be performed:
 - i) Hematology: hemoglobin, hematocrit, mean corpuscular volume (MCV), white blood cell count, differential white blood cell count, and platelet count.
 - ii) Blood chemistries: electrolytes, blood urea nitrogen (BUN), creatinine, glucose, phosphorus, and calcium
 - iii) Liver function tests: total bilirubin, AST, ALT, alkaline phosphatase, and albumin.
 - iv) Coagulation: prothrombin time, international normalized ratio, partial thromboplastin time

- v) Urinalysis, including urine glucose and protein

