12. INFORMED CONSENT

This protocol and the informed consent document and any subsequent modifications will be reviewed and approved by the Institutional Review Board at each participating institution. Written informed consent will be obtained from the subject. Subjects who are unable to provide consent due to neurocognitive impairment or

other causes will not be enrolled. The informed consent will describe the purpose of the study, the procedures to be followed, and the risks and benefits of participation. A copy of the consent form will be given to the subject (or legal guardian). If the potential subject is still interested in participating, a clinic visit will be scheduled. The subject will be informed of the time that needs to be allotted for their first visit in which the informed consent will be administered.

The informed consent will describe the purpose of the study, the procedures to be followed, and the risks, and benefits of participation. This information will be explained to the study subject in a face-to-face setting by the individual consent the subject. Subjects will be encouraged to ask questions throughout the consent process and encouraged to discuss their participation with trusted advisors, such as family members, close friends, etc. Subjects will be allotted sufficient time to consider whether or not to participate in the research study. After allowing the potential subject time to read the informed consent the study staff and/or investigator will answer and address any questions or concerns the subject may have. Once all questions and concerns have been addressed and the subject wishes to participate, they will be asked to sign the informed consent.

Also, during the consent process, the Health Insurance Portability and Accountability Act (HIPAA) Authorization will addressed. A copy of the consent and HIPAA Authorization form as well as the Notice of Privacy Practices booklet will be given to the subject. A subject's bill of rights will also be given to the subject.

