estimated creatinine clearance below 50 ml/min will also have the study drug terminated and complete the evaluations listed in Section 4.2. Subjects will also have the study drug terminated in cases of suspected drug-related toxicity, taking prohibited concomitant medications (see section 4.2 of the master protocol), if a female subject is pregnant or breast-feeding, if the subject is judged by the investigators to be at significant risk of failing to comply with the provisions of the protocol as to cause harm to self or seriously interfere with the validity of the study results, at the discretion of the investigator, institutional review board (IRB), Food and Drug Administration, pharmaceutical sponsor; or if the subject requests to withdraw from the study. In case of injury or serious adverse events, the investigators will assist the subject in obtaining appropriate medical treatment.

Lumbar Punctures: Experienced research clinicians (either a physician or a nurse) will perform all lumbar punctures. Local back pain will be minimized by injection of an anesthetic, 1% lidocaine into the subcutaneous tissue surrounding the needle puncture site. Oral analgesics and anti-inflammatory medications will be provided when necessary. Following LP, patients will be observed for 10-15 minutes. Over 3,000 LPs have been performed at the HNRC using non-cutting or "pencil point" spinal needles that reduce the risk of post-LP cephalgia. A site clinician will be available by pager 24 hours-per-day to respond to problems, should they occur. If post-LP headache occurs, initial conservative management will include recumbency, hydration, and oral analgesics. When headaches are prolonged, a blood patch, involving an epidural injection of a sample of the subject's own blood, may be performed by consulting anesthesiologists.

UCSD AVRC will serve as the lead/coordinating site for this study. Clinics at the Erie County Medical Center and University of Rochester will be subordinate sites, as outlined in the master protocol team roster. All adverse events, protocol deviations, and other study related reports will be reviewed by the PI as outlined in section 5.0 of the Master Protocol. All data transfers and other study related information will be performed in accordance with the Data Security Plan.

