The safety and tolerability of the study medications will also be monitored closely by the protocol team. In addition, a Data Safety Monitoring Board (DSMB) will be convened at two timepoints (after 50% enrollment, after completion of enrollment) to review the project's safety data. At least three experts will comprise the DSMB: a statistician with experience in clinical trials, an expert in HIV clinical trials, and an expert in neurologic HIV disease research. Reports will be prepared by the DSMB and responses will be prepared by the protocol team.

Case report forms (CRF) will be provided for each subject. Subjects must not be identified by name on any study documents. Subjects will be identified by the Patient Identification Number (PID) and Study Identification Number (SID).

All data on the CRF must be legibly recorded in black ink or typed. A correction should be made by striking through the incorrect entry with a single line and entering the correct information adjacent to it. The correction must be initialed and dated by the investigator or a designated, qualified individual. Any requested information that is not obtained as specified in the protocol should have an explanation noted on the CRF as to why the required information was not obtained.

Monitoring

The investigators will review the research records for accuracy, completeness, and legibility. The investigators will also regularly inspect regulatory files to ensure that regulatory requirements are being followed.

The investigator will make study documents (e.g., consent forms, drug distribution forms, case report forms)

and pertinent hospital or clinic records readily available for inspection by the Food and Drug Administration (FDA), as required, for confirmation of the study data.

Serious Adverse Experience (SAE) Reporting

Serious Adverse Experiences will be documented on the Serious Adverse Experience (SAE) Reporting Form and submitted to the sponsor and the IRB within 24 hours of the investigator becoming aware of the event.

Safety Monitoring Plan

A safety monitor will be designated to review safety reports.

Data to be reviewed

On a quarterly basis, the monitor will be provided with reports of the following data:

- All hypersensitivity (e.g., rash) and renal events regardless of grade or causality;
- All ALT grades, concurrent ALT + bilirubin, eosinophilia, rash, and other data that could be associated with drug hypersensitivity reactions;

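### Stribild must stop if creatinine clearance falls below 50 mL/min, but the supplied schedule has no creatinine or eGFR between Week 2 and Week 24 (154 days nominal)

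*Combined protocol and SAP*

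**What the plan says.** The stopping rule appears twice. Under Management of Selected Toxicities in Section 9: "If renal impairment occurs as indicated by a decrease of estimated creatinine clearance below 50 mL/min, study treatment will be discontinued". Section 15 repeats it for subjects whose "estimated creatinine clearance below 50 ml/min will also have the study drug terminated".

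The visit lists in Section 9 place creatinine and eGFR at screening, Week 2 and Week 24. The safety assessment row of the schedule table is marked only at Weeks 2 and 24. Between those two visits, Section 9 (Events Between Week 2 and Week 24 Visits) provides three things:

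- Item a: "The study coordinator will call study subjects at Weeks 8 and 16", and more often at the coordinator's discretion. The calls cover symptoms and adherence, and a clinic evaluation follows if symptoms are reported.
- Item b: "Eight weeks of study drug will be dispensed at Weeks 8 and 16". No laboratory result is a condition for dispensing.
- Item c: subjects are to have plasma HIV RNA measured in routine care and bring the laboratory report to the site. On timing: "This is anticipated to occur after approximately 12 weeks of treatment". Alternatively, "with the consent of the study subject, the research nurse will obtain the value from the clinic". Only HIV RNA is named.

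Under the Safety Monitoring Plan in Section 15, a monitor receives quarterly reports that include all "renal events regardless of grade or causality".

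**The concern.** A rule triggered by a laboratory value works only when that value is measured. After Week 2 the supplied schedule offers no such occasion until the Week 24 visit, which is also the planned end of study treatment. An asymptomatic subject could cross the threshold, be dispensed drug at Weeks 8 and 16, and stay on it until the Week 24 result, with everyone following the plan correctly. The quarterly review does not help here, because it reviews events already found and no scheduled renal test feeds it during this period.

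What is at stake is delay in detecting a condition that the plan itself treats as a reason to stop.

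**Working it through.** The plan does not state the length of the gap, so there is no figure of its own to reproduce. It follows from the schedule.

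**Inputs.** PK1 is on Day 14 and PK2 on Day 168 (Section 9, Drug Regimens, Administration and Duration). The table windows are Days 12–20 for Week 2, 105–119 for Week 16 and 161–175 for Week 24. The Week 12 draw is only approximately timed, so Day 84 is an assumption, varied below.

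**Current gap between scheduled renal values**

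- Nominal: 168 − 14 = 154 days (22 weeks), or 154/168 = 92% of the treatment period.
- Shortest: 161 − 20 = 141 days. Longest: 175 − 12 = 163 days.
- Against the quarterly review: 365.25/4 = 91.3 days, and 141/91.3 = 1.54. At least one quarterly report per subject therefore falls inside the gap, with no scheduled renal value later than Week 2.

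**Gap if a routine-care value exists on Day d.** The longest nominal gap is max(d − 14, 168 − d).

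| Day d (assumed) | d − 14 | 168 − d | Longest |
|---|---|---|---|
| 56 | 42 | 112 | 112 |
| 70 | 56 | 98 | 98 |
| 84 | 70 | 84 | 84 |
| 91 | 77 | 77 | 77 (minimum) |
| 98 | 84 | 70 | 84 |
| 112 | 98 | 56 | 98 |

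For Day 84 with the visit windows, the two parts are 64–72 days (84 − 20 to 84 − 12) and 77–91 days (161 − 84 to 175 − 84). For d between 70 and 98 the longest gap is 77–98 days nominally and 71–105 across the windows (upper end 175 − 70). For d between 56 and 112 it is 77–112 nominally and 71–119 across the windows (upper end 175 − 56). With no value it stays at 154.

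**Would the result come before the Week 16 dispensing (Days 105–119)?**

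- d = 84: 105 − 84 = 21 to 119 − 84 = 35 days before.
- d = 98: 7 to 21 days before.
- d = 112: from 7 days after dispensing to 7 days before it.

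**For comparison,** study creatinine at Weeks 8 and 16 would give nominal gaps of 56 − 14 = 42, 112 − 56 = 56 and 168 − 112 = 56 days for every subject.

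**The case against.** The strongest reply is that this concerns how often to monitor and is no contradiction in the plan. The rule is conditional, sets no testing interval, and the documents contain no standard that the interval breaches. The supplied text is a site research plan that refers to a master protocol for toxicity handling and post-treatment evaluations, and that protocol could contain an interim test. Several safeguards also exist:

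- Entry is limited to ages 18–60 and a clearance of at least 70 mL/min, and chronic illnesses such as hypertension and diabetes are excluded.
- Week 2 covers phosphorus and urinalysis with glucose and protein as well as creatinine and eGFR.
- Calls may be more frequent, a telephone line is open around the clock, and subjects remain under a primary care provider.

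Most of this stands, and it lowers the severity. It does not remove the point, because none of these safeguards measures creatinine on a schedule after Week 2 and before Week 24. The master protocol limits confidence, but nothing in the supplied schedule points to an interim test.

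Two further objections also stand. First, the Week 12 report may already reach the site with a creatinine on it, and nothing restricts the rule to study-laboratory values. What is missing then is a request for the test, a place to record it and an explicit check. Second, the same gap affects the other laboratory-triggered stops in Sections 9 and 15, and a creatinine request does not address those.

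A reader might infer that the consent form must change. The consent pages are not part of the supplied text, so this cannot be shown.

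**Conclusion.** The point holds at low severity. In the supplied text, a mandatory renal stop has no scheduled test to trigger it for 154 days nominally (141–163 across the windows), so a fall without symptoms would surface before Week 24 only through an unscheduled or routine-care value.

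Two stronger readings are tempting. One is that subjects will be harmed, or that some number of missed cases can be expected. The documents give no incidence of renal impairment and the study enrols 14 subjects with adequate renal function at entry, so only the possible delay can be stated. The other is that using the Week 12 report closes the gap. It does not: it guarantees no value, and the reduction from 154 to 84 days applies only where routine care measured creatinine at about the assumed day.

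The conclusion rests on the supplied schedule being complete. If the master protocol adds an interim creatinine, the point falls.

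**What to change.** First check the master protocol for an interim creatinine. If there is none, amend item c of the between-visit events in Section 9 as follows:

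1. Subjects ask their primary care provider to include serum creatinine in the routine draw already expected at about Week 12.
2. The site collects any creatinine or eGFR on that report, or retrieves it together with the HIV RNA value.
3. Staff record it on the CRF and check it against the 50 mL/min rule on receipt, and before the Week 16 dispensing if it is available by then.
4. Consent wording is adjusted only if the existing wording does not cover this retrieval.

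**Cost.** A few CRF fields and a short wording change. Section 12 says of the protocol and consent document that "any subsequent modifications will be reviewed and approved by the Institutional Review Board at each participating institution", so each IRB must see it. No study visit, study procedure or staff is added. Section 19 promises that participation costs the subject nothing, so the team should settle who pays if a provider orders creatinine only because the study asked.

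**Downside.** Coverage is partial and depends on routine care, and a check before the Week 16 dispensing is not assured. Study creatinine at Weeks 8 and 16 would cover every subject but adds two blood draws that the plan does not have, so it is not proposed here.
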